15.9 Abuse, Misuse, or Medication Error

Abuse is the persistent or sporadic, intentional excessive use of the study drug which is accompanied by harmful physical or psychological effects.

A medication error is any preventable incident that may cause or lead to inappropriate medication use or patient harm while the medication is in the control of the health care

professionals or patients. Such incident may be due to health care professional practice, product labeling, packaging and preparation, procedures for administration, and systems, including prescribing; order communication; and nomenclature; compounding; dispensing; distribution; administration; education; monitoring; and use.'

All occurrences of abuse, misuse or medication error with Karyopharm drug are to be reported on an FDA 3500A MedWatch form to the DSMC and Karyopharm pharmacovigilance regardless of whether or not an AE or SAE has occurred due to the abuse, misuse or medication error. If the abuse, misuse or medication error is associated with an SAE, the SAE report form must be submitted to the DSMC and Karyopharm pharmacovigilance within 24 hours of awareness. If there is no AE or SAE, the report must be submitted as soon as possible. In all cases, the IRB and the FDA must be notified as applicable.

15.10 Occupational Exposure

Occupational exposure is the exposure to a study drug as a result of one's professional or non-professional occupation.

All occurrences of occupational exposure with Karyopharm drug are to be reported on an FDA 3500A MedWatch form to the DSMC and Karyopharm pharmacovigilance regardless of whether or not an AE or SAE has occurred due to the occupational exposure. If the occupational exposure is associated with an SAE, the SAE report form must be submitted to the DSMC and Karyopharm pharmacovigilance within 24 hours of awareness. If there is no AE or SAE, the report must be submitted as soon as possible. In all cases, the IRB and the FDA must be notified as applicable.

15.11 Protocol Amendments

Any amendments or administrative changes in the research protocol during the period, for which the IRB approval has already been given, will not be initiated without submission of an amendment for IRB review and approval.

These requirements for approval will in no way prevent any immediate action from being taken by the investigator in the interests of preserving the safety of all subjects included in the trial.

Any amendments to the protocol that significantly affect the safety of subjects, scope of the investigation, or the scientific quality of the study are required to submit the amendment for FDA review.

15.12 Protocol Deviations

A protocol deviation (or violation) is any departure from the defined procedures and treatment plans as outlined in the protocol version submitted and previously approved by the IRB. Protocol deviations have the potential to place participants at risk and can also undermine the scientific integrity of the study thus jeopardizing the justification for the research. Protocol deviations are unplanned and unintentional events.

Because some protocol deviations pose no conceivable threat to participant safety or scientific integrity, reporting is left to the discretion of the PI within the context of the guidelines below. The IRB requires the **prompt reporting** of protocol deviations which are:

- Exceptions to eligibility criteria.
- Intended to eliminate apparent immediate hazard to a research participant or
- Harmful (caused harm to participants or others, or place them at increased risk of harm - including physical, psychological, economic, or social harm), or
- Possible serious or continued noncompliance

15.13 FDA Annual Reporting

An annual progress report will be submitted to the FDA within 60 days of the anniversary of the date that the IND went into effect. (21 CFR 312.33).

15.14 Clinical Trials Data Bank

The study will be registered on <http://clinicaltrials.gov> and the NCI CTRP (Clinical Trials Reporting Program) by the Clinical Trials Office.

15.15 Record Keeping

Per 21 CFR 312.57, the Investigator records shall be maintained for a period of 2 years following the date a marketing application is approved; or, if no application is filed or the application is not approved, until 2 years after the investigation is discontinued and the FDA is notified.

16 APPENDICES

16.1 Appendix 1 - Eastern Cooperative Oncology Group Performance Status Criteria (ECOG) & Karnofsky Performance Scale Index (KPS) equivalency

ECOG Performance Status Scale ¹		Karnofsky Performance Scale ²	
Grade	Descriptions	Percent	Description
0	Normal activity. Fully active, able to carry on all pre-disease performance without restriction.	100	Normal, no complaints, no evidence of disease.
		90	Able to carry on normal activity; minor signs or symptoms of disease.
1	Symptoms, but ambulatory. Restricted in physically strenuous activity, but ambulatory and able to carry out work of a light or sedentary nature (e.g., light housework, office work).	80	Normal activity with effort; some signs or symptoms of disease.
		70	Cares for self, unable to carry on normal activity or to do active work.
2	In bed < 50% of the time. Ambulatory and capable of all self-care, but unable to carry out any work activities. Up and about more than 50% of waking hours.	60	Requires occasional assistance but is able to care for most of his/her needs.
		50	Requires considerable assistance and frequent medical care.
3	In bed >50% of the time. Capable of only limited self-care, confined to bed or chair more than 50% of waking hours.	40	Disabled, requires special care and assistance.
		30	Severely disabled, hospitalization indicated. Death not imminent.
4	100% bedridden. Completely disabled. Cannot carry on any self-care. Totally confined to bed or chair.	20	Very sick, hospitalization indicated. Death not imminent.
		10	Moribund, fatal processes progressing rapidly.
5	Dead.	0	Dead.

16.2 Appendix 2 - Ophthalmic Exam

An ophthalmic examination by an optometrist or ophthalmologist is optional at screening and if clinically indicated during the study (e.g., monitoring of pre-existing cataracts, visual disturbances).

The optional examination is to include the following:

Prior to dilation:

- Best corrected visual acuity
- Slit lamp examination
- Tonometry

Following dilation:

- Fundoscopy
- Slit lamp examination to document lens clarity

If a cataract/lens opacity is seen during the examination, the cataract/lens opacity will be graded according to a Grade 1-4 system (modified from Optometric Clinical Practice Guideline: Care of the Adult Patient with Cataracts: available on the American Optometric Association website: www.aoa.org).

Grading of Cataracts*				
Cataract Type	Grade 1	Grade 2	Grade 3	Grade 4
Nuclear Yellowing and sclerosis of the lens nucleus	Mild	Moderate	Pronounced	Severe
Cortical Measured as aggregate percentage of the intrapupillary space occupied by the opacity	Obscures 10% of intrapupillary space	Obscures 10% - 50% of intrapupillary space	Obscures 50% - 90% of intrapupillary space	Obscures >90% of intrapupillary space
Posterior subcapsular Measured as the aggregate percentage of the posterior capsular area occupied by the opacity	Obscures 10% of the area of the posterior capsule	Obscures 30% of the area of the posterior capsule	Obscures 50% of the area of the posterior capsule	Obscures >50% of the area of the posterior capsule

*Designation of cataract severity that falls between grade levels can be made by addition of a + sign (e.g., 1+, 2+). Grading of cataracts is usually done when pupil is dilated.

16.3 Appendix 3 - NCCN Clinical Practice Guidelines in Oncology: Antiemesis

Available at http://www.nccn.org/professionals/physician_gls/PDF/antiemesis.pdf.

Reproduced with permission from the NCCN Clinical Practice Guidelines in Oncology (NCCN Guidelines®) for **Antiemesis V.2.2020**. © 2020 National Comprehensive Cancer Network, Inc. All rights reserved. The NCCN Guidelines® and illustrations herein may not be reproduced in any form for any purpose without the express written permission of the NCCN. To view the most recent and complete version of the NCCN Guidelines, go online to www.nccn.org. NATIONAL COMPREHENSIVE CANCER NETWORK®, NCCN®, NCCN GUIDELINES®, and all other NCCN Content are trademarks owned by the National Comprehensive Cancer Network, Inc.

Available at http://www.nccn.org/professionals/physician_gls/PDF/antiemesis.pdf.

Reproduced with permission from the NCCN Clinical Practice Guidelines in Oncology (NCCN Guidelines®) for **Antiemesis V.2.2020**. © 2020 National Comprehensive Cancer Network, Inc. All rights reserved. The NCCN Guidelines® and illustrations herein may not be reproduced in any form for any purpose without the express written permission of the NCCN. To view the most recent and complete version of the NCCN Guidelines, go online to www.nccn.org. NATIONAL COMPREHENSIVE CANCER NETWORK®, NCCN®, NCCN GUIDELINES®, and all other NCCN Content are trademarks owned by the National Comprehensive Cancer Network, Inc.

**16.4 Appendix 4 - NCCN Clinical Practice Guidelines in Oncology:
Anorexia/Cachexia**

Reproduced with permission from the NCCN Clinical Practice Guidelines in Oncology (NCCN Guidelines®) for **Palliative Care V.1.2020**. © 2020 National Comprehensive Cancer Network, Inc. All rights reserved. The NCCN Guidelines® and illustrations herein may not be reproduced in any form for any purpose without the express written permission of the NCCN. To view the most recent and complete version of the NCCN Guidelines, go online to www.nccn.org. NATIONAL COMPREHENSIVE CANCER NETWORK®, NCCN®, NCCN GUIDELINES®, and all other NCCN Content are trademarks owned by the National Comprehensive Cancer Network, Inc.

16.5 Appendix 5 - International Working Group-Myeloproliferative Neoplasms Research and Treatment (IWG-MRT) Criteria for myelofibrosis

Response Categories	Required Criteria (for All Response Categories, Benefit Must Last for \geq 12 Weeks to Qualify as a Response)
CR	Bone marrow ¹ : Age-adjusted normocellularity; <5% blasts; \leq Grade 1 MF ² and
	Peripheral blood: Hemoglobin \geq 100 g/L and < UNL; neutrophil count $\geq 1 \times 10^9/L$ and < UNL;
	Platelet count $\geq 100 \times 10^9/L$ and < UNL; < 2% immature myeloid cells ³ and
	Clinical: Resolution of disease symptoms; spleen and liver not palpable; no evidence of EMH
PR	Peripheral blood: Hemoglobin \geq 100 g/L and < UNL; neutrophil count $\geq 1 \times 10^9/L$ and < UNL; platelet count $\geq 100 \times 10^9/L$ and < UNL; < 2% immature myeloid cells ³ and
	Clinical: Resolution of disease symptoms; spleen and liver not palpable; no evidence of EMH or
	Bone marrow: ¹ Age-adjusted normocellularity; < 5% blasts; \leq Grade 1 MF ² ; and peripheral blood: hemoglobin ≥ 85 g/L but < 100 g/L and < UNL; neutrophil count $\geq 1 \times 10^9/L$ and < UNL; platelet count $\geq 50 \times 10^9/L$ but < $100 \times 10^9/L$ and < UNL; < 2% immature myeloid cells ³ and
	Clinical: Resolution of disease symptoms; spleen and liver not palpable; no evidence of EMH
CI	The achievement of anemia, spleen or symptoms response without progressive disease or increase in severity of anemia, thrombocytopenia, or neutropenia ⁴
Anemia Response	Transfusion-independent patients: a ≥ 20 g/L increase in hemoglobin level ⁵
	Transfusion-dependent patients: becoming transfusion-independent ⁶
Spleen Response ⁷	A baseline splenomegaly that is palpable at 5-10 cm, below the LCM, becomes not palpable ⁸ or
	A baseline splenomegaly that is palpable at > 10 cm, below the LCM, decreases by $\geq 50\%$ ⁸
	A baseline splenomegaly that is palpable at < 5 cm, below the LCM, is not eligible for spleen response
	A spleen response requires confirmation by MRI or CT showing $\geq 35\%$ spleen volume reduction
Symptoms response	A $\geq 50\%$ reduction in the MPN-SAF TSS ⁹
Progressive disease ¹⁰	Appearance of a new splenomegaly that is palpable at least 5 cm below the LCM or
	A $\geq 100\%$ increase in palpable distance, below LCM, for baseline splenomegaly of 5-10 cm or
	A 50% increase in palpable distance, below LCM, for baseline splenomegaly of > 10 cm or
	Leukemic transformation confirmed by a bone marrow blast count of $\geq 20\%$ or A peripheral blood blast content of $\geq 20\%$ associated with an absolute blast count of $\geq 1 \times 10^9/L$ that lasts for at least 2 weeks
Stable Disease	Belonging to none of the above-listed response categories
Relapse	No longer meeting criteria for at least CI after achieving CR, PR, or CI, or
	Loss of anemia response persisting for at least 1 month or
	Loss of spleen response persisting for at least 1 month

Abbreviations: LCM = left costal margin; MF = myelofibrosis; MPN-SAF TSS = Myeloproliferative Neoplasm Symptom Assessment Form Total Symptom Score; MRI = magnetic resonance imaging; PR = partial response; PRBC = packed red blood cell; UNL = upper normal limit.

1. Baseline and post-treatment bone marrow slides are to be interpreted at 1 sitting by a central review process. Cytogenetic and molecular responses are not required for CR assignment.
2. Grading of MF is according to the European classification.^a It is underscored that the consensus definition of a CR bone marrow is to be used only in those patients in which all other criteria are met, including resolution of leukoerythroblastosis. It should also be noted that it was a particularly difficult task for the working group to reach a consensus regarding what represents a complete histologic remission.
3. Immature myeloid cells constitute blasts + promyelocytes + myelocytes + metamyelocytes + nucleated red blood cells. In splenectomized patients, < 5% immature myeloid cells is allowed.
4. See above for definitions of anemia response, spleen response, and progressive disease. Increase in severity of anemia constitutes the occurrence of new transfusion dependency or a ≥ 20 g/L decrease in hemoglobin level from pretreatment baseline that lasts for at least 12 weeks. Increase in severity of thrombocytopenia or neutropenia is defined as a 2-grade decline, from pretreatment baseline, in platelet count or absolute neutrophil count, according to the CTCAE version 5.0. In addition, assignment to CI requires a minimum platelet count of $\geq 25,000 \times 10^9/L$ and absolute neutrophil count of $\geq 0.5 \times 10^9/L$.
5. Applicable only to patients with baseline hemoglobin of < 100 g/L. In patients not meeting the strict criteria for transfusion dependency at the time of study enrollment (see as follows), but have received transfusions within the previous month, the pretransfusion hemoglobin level should be used as the baseline.
6. Transfusion dependency before study enrollment is defined as transfusions of at least 6 units of PRBCs, in the 12 weeks prior to study enrollment, for a hemoglobin level of < 85 g/L, in the absence of bleeding or treatment-induced anemia. In addition, the most recent transfusion episode must have occurred in the 28 days prior to study enrollment. Response in transfusion-dependent patients requires absence of any PRBC transfusions during any consecutive "rolling" 12-week interval during the treatment phase, capped by a hemoglobin level of ≥ 85 g/L.
7. In splenectomized patients, palpable hepatomegaly is substituted with the same measurement strategy.
8. Spleen or liver responses must be confirmed by imaging studies where a $\geq 35\%$ reduction in spleen volume, as assessed by MRI or CT, is required. Furthermore, a $\geq 35\%$ volume reduction in the spleen or liver, by MRI or CT, constitutes a response regardless of what is reported with physical examination.
9. Symptoms are evaluated by the MPN-SAF TSS. The MPN-SAF TSS is assessed by the patients themselves and this includes fatigue, concentration, early satiety, inactivity, night sweats, itching, bone pain, abdominal discomfort, weight loss, and fevers. Scoring is from 0 (absent/as good as it can be) to 10 (worst imaginable/as bad as it can be) for each item. The MPN-SAF TSS is the summation of all the individual scores (0-100 scale). Symptoms response requires $\geq 50\%$ reduction in the MPN-SAF TSS.
10. Progressive disease assignment for splenomegaly requires confirmation by MRI or CT showing a $\geq 25\%$ increase in spleen volume from baseline. Baseline values for both physical examination and imaging studies refer to pretreatment baseline and not to post-treatment measurement.
 - a. Thiele J, Kvasnicka HM, Facchetti F, van der Walt J, Orazi A. European consensus on grading bone marrow fibrosis and assessment of cellularity. *Haematologica*. 2005;90(8):1128-32.

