10.2.3 Overall Response

Overall response criteria are based on the 2013 International Working Group-Myeloproliferative Neoplasms Research and Treatment (IWG-MRT) Criteria for myelofibrosis (listed in Appendix 5).²⁶

The overall response rate (CR, PR, CI) from after six cycles of treatment is defined in Appendix 5.

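### Appendix 5 prints the platelet minimum for the CI response category as 25,000 × 10⁹/L, which no patient can reach, so the secondary overall response rate read literally is CR + PR only

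*Combined protocol and SAP*

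**What the plan says.** Section 1.2.2 lists overall response by the 2013 IWG-MRT criteria as a secondary endpoint. Section 10.2.3 passes the definition to the appendix: "The overall response rate (CR, PR, CI) from after six cycles of treatment is defined in Appendix 5". Section 11.5.2 reports it as a count and proportion with an exact 95% binomial interval.

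In Appendix 5 the CI row reads "The achievement of anemia, spleen or symptoms response without progressive disease or increase in severity of anemia, thrombocytopenia, or neutropenia" and carries footnote 4. The last sentence of that footnote adds two blood-count conditions. For platelets, "assignment to CI requires a minimum platelet count of $\geq 25,000 \times 10^9/L". For neutrophils, "absolute neutrophil count of $\geq 0.5 \times 10^9/L".

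The other platelet limits in the appendix use the same unit. CR requires "Platelet count $\geq 100 \times 10^9/L$ and < UNL", and the first PR route has the same limits. The second PR route requires "platelet count $\geq 50 \times 10^9/L$ but < $100 \times 10^9/L$ and < UNL". Section 5.1.6 admits patients with platelets of 30,000/mm³ or more.

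**The concern.** The number 25,000 is of the size used for counts per mm³, but it is printed with the multiplier × 10⁹/L. CI is the least demanding of the three categories in the overall response rate, yet as printed it needs far more platelets than CR, which itself has a ceiling at the upper normal limit.

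This is more than a typographical matter because Appendix 5 is the operative definition of a named secondary endpoint. CI is also the component most open to partial benefit. CR and both PR routes require disease symptoms to have resolved and the spleen and liver to be impalpable, whereas every eligibility route in section 5.1.5 requires a spleen palpable at least 5 cm below the costal margin. A patient with only an anemia, spleen or symptoms response can enter the overall rate through CI alone.

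**Working it through.** **Inputs**

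- CI platelet minimum as printed: 25,000 × 10⁹/L (Appendix 5, footnote 4).
- CI neutrophil minimum: 0.5 × 10⁹/L (same sentence).
- CR platelet floor: 100 × 10⁹/L (Appendix 5).
- Second PR route: 50 to below 100 × 10⁹/L (Appendix 5).
- Entry criteria: platelets 30,000/mm³, neutrophils 500/mm³ (section 5.1.6).

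**Step 1: common unit.** One litre is 10⁶ mm³, so 1 × 10⁹/L = 1,000/mm³.

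- Printed CI platelet minimum: 25,000 × 10⁹ / 10⁶ = 25,000,000/mm³.
- Entry platelets: 30,000 × 10⁶ / 10⁹ = 30 × 10⁹/L.
- CI neutrophil minimum: 0.5 × 10⁹ / 10⁶ = 500/mm³, the same as the entry neutrophil criterion. This half of the sentence is on the right scale.

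**Step 2: comparison with the plan's other platelet limits**

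| Limit | × 10⁹/L | Printed CI minimum ÷ limit |
|---|---|---|
| CR floor | 100 | 25,000/100 = 250 |
| Second PR route, floor | 50 | 25,000/50 = 500 |
| Entry criterion | 30 | 25,000/30 ≈ 833 |

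Dividing the printed number by 1,000 gives 25 × 10⁹/L = 25,000/mm³, below all three limits. That removes the contradiction, but it does not prove that 25 × 10⁹/L was intended.

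**Step 3: effect on the overall response rate.** If no patient can meet the minimum, CI is empty and CR + PR + CI becomes CR + PR. Section 11.4.2 makes the efficacy population all enrolled patients with at least one dose. Assume 24 are treated, the planned maximum. Each CI-only responder lost then lowers the rate by 1/24 = 4.2 percentage points, whatever the CR + PR count.

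For illustration, take no CR or PR and x CI-only responders. The exact (Clopper-Pearson) limits are the 2.5% quantile of Beta(x, 24 − x + 1) and the 97.5% quantile of Beta(x + 1, 24 − x), with the lower limit 0 when x = 0. The counts are assumed and are not forecasts.

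| CI-only responders | Rate with a usable minimum (95% interval) | Rate as printed (95% interval) |
|---|---|---|
| 1 | 4.2% (0.1 to 21.1) | 0% (0 to 14.2) |
| 3 | 12.5% (2.7 to 32.4) | 0% (0 to 14.2) |
| 6 | 25.0% (9.8 to 46.7) | 0% (0 to 14.2) |

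**Step 4: what is not affected.** The primary response is a spleen volume reduction of 35% or more, with no platelet or CI condition. The section 11.2 design reproduces: with 18 patients and rejection at 6 or more responders, the exact one-sided error at 15% is 0.0419 and the power at 42% is 0.837, against the stated 83%. Percent change in spleen volume, the symptom-score endpoint and overall survival do not use CI either.

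**Step 5: other uses of the category.** The first of three alternatives for relapse is "No longer meeting criteria for at least CI after achieving CR, PR, or CI, or", so it inherits the error, but relapse is not a named endpoint in section 1. The Study Summary also plans a time-to-response summary that may cover overall response; sections 1.2 and 11.5.2 do not mention it. Whether a spleen responder refused CI would be classed as stable disease is unclear, because footnote 8 says that a volume reduction of 35% or more "constitutes a response regardless of what is reported with physical examination".

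**The case against.** The strongest reply is that nobody would apply the figure. It is physiologically impossible, the neighbouring limits expose it, and sections 1.2.2 and 10.2.3 name the published criteria against which it can be checked. On that view this is an editorial correction to a descriptive endpoint, the illustrative counts show nothing about actual impact, and the effects on relapse and time to response are slight.

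Much of this stands. The loss occurs only if the figure is applied literally, the counts are assumed, the further effects are side issues, and the intended value can only be inferred.

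It does not remove the need for a correction. The protocol prints no usable CI platelet minimum, so an assessor who sees the slip must supply a number from elsewhere. Sections 10.2.1 to 10.2.3 cite the criteria as reference 26, whereas the reference list in the copy reviewed ends at 23. The exact limit may also matter in this population: patients can enter at 30 × 10⁹/L, and section 3.1.4 reports thrombocytopenia at least possibly related to selinexor in 52.1% of patients. Some could lie close to any plausible minimum, where different guesses would give different classifications.

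**Conclusion.** The footnote is wrong as written. The contradiction is established from the protocol's own limits and does not depend on any outside source. Taken literally, it makes CI unattainable and turns the secondary overall response rate into CR + PR, a loss of 4.2 percentage points per CI-only responder if 24 patients are treated.

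Severity is low: the endpoint is descriptive with no hypothesis test, many assessors would probably notice the error, and the primary analysis is untouched. Confidence is high that the printed figure is inconsistent. It does not extend to 25 × 10⁹/L as the intended value, which the sponsor has to confirm.

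**What to change.** Restate the platelet minimum in footnote 4 in the unit used elsewhere in Appendix 5, after the sponsor has confirmed the value against the 2013 IWG-MRT criteria. The likely value is 25 × 10⁹/L (25,000/mm³), but the documents do not print it and it should not be adopted without that check. Then review CI decisions already made, including any patient refused CI on platelet grounds, against the confirmed value before the overall response rate is analysed.

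The cost is one corrected figure in an appendix footnote and a short review of existing response assignments. Design, sample size and data collection do not change.

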6.3.1 Allowed Therapy

Any medication which is considered necessary for a subject's welfare is permitted and may be given at the discretion of the investigator. Medications for treatment of underlying disease and symptomatic treatment of adverse events are permitted. Exceptions are listed in the section below.

Use of Blood Products

During treatment, patients may receive red blood cell (RBC) or platelet transfusions, if clinically indicated, per institutional guidelines.

Appropriate anti-coagulation is allowed during the study (e.g., low molecular weight heparin, direct factor Xa inhibitors, etc.). Warfarin is allowed during the study provided patients are monitored for INR twice a week during the first two cycles of therapy, then weekly to biweekly. Patients may receive supportive care with erythropoietin, darbepoetin, granulocyte-colony stimulating factor or granulocyte macrophage-colony stimulating factor, pegylated growth factors, and platelet stimulatory factors, in accordance with clinical practice or institutional guidelines prior to entry and throughout the study.

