Grade ≥ 3 with bleeding	
Interrupt selinexor dosing and check platelet counts weekly until the bleeding has stopped, patient is clinically stable and the platelets have recovered to Grade ≤ 3 or baseline. Platelet transfusion is allowed if clinically indicated at the discretion of the principal investigator. When resuming selinexor, reduce by 1 dose level.
 
If recurrent, unless contraindicated, start treatment with moderate to high doses of thrombopoietin stimulating agents as above.

Neutropenia	
Grade 4 neutropenia (afebrile) OR Febrile neutropenia	
Institute colony stimulating factors and prophylactic antibiotics as clinically indicated per institutional guidelines.
 
Interrupt selinexor and check neutrophils at least weekly until recovers to Grade 3 or baseline and without fever (if febrile) and the patient is clinically stable. Colony stimulating factors per institutional guidelines or at the discretion of the principal investigator. When resuming selinexor, reduce by 1 dose level.
 
If recurrent, continue colony stimulating factors, interrupt selinexor until neutrophil counts improve to Grade ≤ 3 or baseline levels. Investigator in consultation with the Medical Monitor may decide to continue selinexor dosing without dose reductions as specified above, provided that CBC and infection symptoms/signs are closely monitored.

Anemia	
Treat per institutional guidelines including blood transfusions and/or erythropoietins. Consider transfusing for symptoms with hemoglobin > 8 g/dL (Grade < 3) or for any Grade 3 (hemoglobin < 8 g/dL). If possible, maintain selinexor dose as long as patient is clinically stable, but if a dose reduction or interruption is desired, it should be done at the discretion of the treating physician and requires authorization from the principal investigator and consultation with the medical monitor if indicated.	
Other clinically significant selinexor-related adverse events	
Grade 1 or 2	Rule out other causes. Maintain dose. Start treatment and/or standard supportive care per institutional guidelines.
Grade 3	
Rule out other causes. Interrupt selinexor until recovers to Grade 2 or baseline and reduce selinexor by 1 dose level.
 
Isolated values of Grade 3 alkaline phosphatase do NOT require dose interruption. Determination of liver versus bone etiology should be made, and evaluation of gamma-glutamyl transferase, 5'-nucleotidase, or other liver enzymes should be performed.

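### Anaemia response in patients not transfusion-dependent at entry has no transfusion-free condition on study, so repeated transfusion below the dependency threshold could count towards the overall response rate

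*Combined protocol and SAP*

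**What the plan says.** Appendix 5 (16.5) gives two routes to an anaemia response, and its table header requires every benefit to last at least 12 weeks.

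- **Not transfusion-dependent.** The criterion is a rise of at least 20 "g/L increase in hemoglobin level". Note 5 limits this to baseline haemoglobin below 100 g/L. For patients who miss the dependency definition "but have received transfusions within the previous month", it adds that "the pretransfusion hemoglobin level should be used as the baseline".
- **Transfusion-dependent.** The patient must become transfusion-independent. Note 6: "Response in transfusion-dependent patients requires absence of any PRBC transfusions during any consecutive" rolling 12-week interval, ending with haemoglobin of at least 85 g/L.

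Note 6 defines dependency, for the period before enrolment, as at least 6 red-cell units in 12 weeks for haemoglobin below 85 g/L, leaving aside bleeding and treatment-induced anaemia. Note 4 withholds clinical improvement if new transfusion dependency occurs.

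An anaemia response alone gives clinical improvement, and 10.2.3 counts that category in the overall response rate. Section 11.5.2 reports the rate with an exact 95% confidence interval and does not mention transfusion.

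Section 6.3.1 states: "During treatment, patients may receive red blood cell (RBC) or platelet transfusions, if clinically indicated, per institutional guidelines". The anaemia entry of Table 4 (7.2) adds: "Consider transfusing for symptoms with hemoglobin > 8 g/dL (Grade < 3").

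**The concern.** Appendix 5 does not accept transfused haemoglobin as a baseline in recently transfused patients, nor transfused weeks as evidence of response in dependent patients. Between these two rules lies a group for whom on-study transfusion is not addressed: anaemic at baseline, but below the dependency threshold. In that group an untransfused baseline can be compared with a transfused follow-up value.

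Such patients are plausible here. Entry is open from haemoglobin 7 g/dL (5.1.6), and 7.2 describes anaemia caused by selinexor and advises considering transfusion when it is symptomatic. The error can only add responders, and a single-arm trial has no control group in which the same error would appear. At stake is the interpretation of a named secondary endpoint (1.2.2).

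**Working it through.** **The plan's own figure.** The only stated design calculation is for spleen response. With X binomial, n = 18 and rejection at 6 or more:

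- alpha = P(X ≥ 6 | p = 0.15) = 0.0419
- power = P(X ≥ 6 | p = 0.42) = 0.837, against 83% stated
- 18 / (1 − 0.25) = 24

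This reproduces, and it uses no haemoglobin value. The overall response rate has no target or sample-size figure.

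**Do the existing limits close the gap?**

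- The 12-week rule requires duration. It does not require the 12 weeks to be free of transfusion.
- The note 4 bar depends on dependency. If note 6's definition is carried on study, up to 5 units in 12 weeks do not reach it, nor do units given at 85 g/L or above. Units given for treatment-induced anaemia would also be left out.

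**Can transfusion below the threshold hold a 20 g/L rise for 12 weeks?** The documents give no increment per unit and no red-cell survival, so these are assumptions: r = 8, 10 or 12 g/L per unit; transfused cells lost linearly over L = 60, 90 or 110 days; the patient's own production constant; u units evenly spaced over 84 days.

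Rise at time t = sum over past units of r × max(0, 1 − age/L).

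Worked case, u = 5, r = 10, L = 90. Units are 84/5 = 16.8 days apart, so just before the next one the ages are 16.8, 33.6, 50.4, 67.2 and 84 days. The remaining fractions are 0.813 + 0.627 + 0.440 + 0.253 + 0.067 = 2.20, giving a trough rise of 22.0 g/L (22.1 on a daily grid).

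Steady-state trough over the nine combinations of r and L, on a daily grid:

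| Units per 12 weeks | Range of trough rise (g/L) | Combinations at 20 g/L or more |
|---|---|---|
| 3 | 5.1 to 18.0 | 0 of 9 |
| 4 | 7.9 to 26.2 | 3 of 9 |
| 5 | 10.6 to 33.6 | 5 of 9 |

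Fewer than 3 units give less again. One of the three four-unit cases is marginal: r = 12, L = 90 gives 12 × (0.767 + 0.533 + 0.300 + 0.067) = 20.0 at the exact trough and 20.5 on the daily grid.

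**Effect on the rate.** One patient is 1/24 = 4.2 points (1/18 = 5.6 if 18 were the denominator). As an illustration only:

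| Responders of 24 | Rate | Exact 95% confidence interval |
|---|---|---|
| 6 | 25.0% | 9.8 to 46.7 |
| 5 (one reclassified) | 20.8% | 7.1 to 42.2 |
| 4 (two reclassified) | 16.7% | 4.7 to 37.4 |

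**The case against.** A reader might infer that a few units are enough, since 20/12 = 1.7 to 20/8 = 2.5 units give an immediate 20 g/L. The documents do not support that: the benefit must last 12 weeks, and 3 units failed in every combination tried. The route is a narrow band just under the 6-unit threshold.

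Other limits also stand:

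- From a baseline at the 70 g/L entry floor, a qualifying patient must stay at 70 + 20 = 90 g/L or more. Table 4 describes transfusion as usual below 8 g/dL and as something to consider for symptoms above it. Top-ups at 90 g/L are permitted but are not the usual case described. This limit is weaker after recent transfusion. Section 5.1.6 lists a delay before screening bloods for growth factors only, so a pre-transfusion baseline can lie below 70 g/L; at 85 − 20 = 65 g/L or lower, a level of 85 g/L is enough.
- Blood counts are taken weekly after the first dose in cycle 1 up to day 22, then on days 1 and 15 of cycles 2 to 6, so troughs would mostly be seen before the six-cycle assessment. Three-monthly visits begin only at cycle 7. But a trough that stays 20 g/L above baseline still qualifies, whether seen or not.
- Note 5 substitutes the pre-transfusion value only for patients transfused in the previous month. It is not a general baseline rule.
- The endpoint is the published 2013 IWG-MRT response. An added condition makes it a modified endpoint, and excluding every transfused patient could remove a genuine responder transfused for bleeding. This is a fair point against an unqualified fix and is met by reporting both counts.

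**Conclusion.** The gap is real but limited. As written, the criteria can count a transfusion-supported rise as an anaemia response, hence as clinical improvement and overall response, in patients with baseline haemoglobin below 100 g/L who are not transfusion-dependent at entry. The bias runs one way.

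That about 4 to 5 units per 12 weeks could do this rests wholly on the assumed increments, red-cell survival and constant production; under less favourable assumptions even 5 units fall short. The 4.2 points per patient is a maximum, because a patient who also has a spleen or symptoms response stays in the rate. The documents do not show how many patients, if any, are affected.

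A reader might go further and infer that the trial's main conclusion is at risk. It is not. The overall response rate is descriptive, with no hypothesis or decision rule, and the primary spleen-volume test, its alpha, power and sample size are untouched.

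**What to change.** In 10.2.3 and 11.5.2, state before responses are classified that:

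1. a rise of at least 20 g/L counts as an anaemia response only if no red cells were given during the 12-week interval that supports it;
2. transfusion for documented bleeding in that interval is flagged and handled by a rule fixed in advance;
3. the overall response rate is also reported under the unmodified IWG-MRT wording, and the patients whose classification differs are listed.

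This extends to the other patients a condition that note 6 already sets for dependent ones. It is an analysis rule only and changes nothing about when patients are transfused.

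The cost is a few sentences. Section 6.3 already requires therapeutic procedures to be recorded with dates; the study team should confirm that red-cell transfusions given between the three-monthly visits are captured too. The main rate may be slightly lower, and it becomes a modified IWG-MRT endpoint that is less directly comparable with published rates. Reporting both counts deals with that.
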